5.3 Subject Recruitment, Enrollment and Screening

- From the Principal Investigator or Co-Investigator clinical practices
- Screening requirements or qualifying lab values
- Evaluation and documentation of inclusion/exclusion criteria

5.4 Early Withdrawal of Subjects

5.4.1 When and How to Withdraw Subjects

- Subject safety issues

- Failure of subject to adhere to protocol requirements
- Disease progression
- Subject decision to withdraw from the study (withdrawal of consent)

Subjects who withdraw from the study for any reason will have their information recorded at the time of withdrawal. At the time of withdrawal, the subject will be considered at the final treatment date and will move into the treatment observation phase (4 weeks). Subjects will not be replaced. Follow up for subjects will continue to follow the normal follow up (Table-2)

5.4.2 Data Collection and Follow-up for Withdrawn Subjects

[figure not shown]
At the time of withdrawal, the reason for withdrawal will be recorded in the CRF. Individuals who withdraw will go into the observation phase for 4 weeks. If a subject withdraws consent, attempts will be made to obtain permissions to collect follow up information.

6 Study Drug

6.1 Description

The chemical name of INCB018424 phosphate is (R)-3-(4-(7H-pyrrolo[2,3-d]pyrimidin-4-yl)-1H-pyrazol-1-yl)-3-cyclopentylpropanenitrile phosphate (Figure 1). INCB018424 phosphate has a molecular formula of C₁₇H₂₁N₆O₄P and a molecular weight of 404.36.

INCB018424 Phosphate Structural Formula

INCB018424 phosphate drug substance is a white to off-white to light pink powder. INCB018424 PHOSPHATE CREAM has been formulated in 4 strengths (0.15%, 0.5%, 1.0%, and 1.5% w/w free base equivalent) that are actively being investigated. All excipients in both the INCB018424 PHOSPHATE CREAM and placebo cream formulations are compendial grade or are approved for use in topical products.

INCB018424 PHOSPHATE CREAM is a topical formulation of an investigational product under development for the treatment of patients with psoriasis, alopecia areata, atopic dermatitis, and other potential autoimmune diseases of the skin. INCB018424 phosphate (ruxolitinib) is an inhibitor of the Janus kinase (JAK) family of protein tyrosine kinases. INCB018424 inhibits Janus Associated Kinases (JAKs) JAK1 and JAK2 which mediate the signaling of a number of

cytokines and growth factors that are important for hematopoiesis and immune function. JAK signaling involves recruitment of STATs (signal transducers and activators of transcription) to cytokine receptors, activation and subsequent localization of STATs to the nucleus leading to modulation of gene expression. Mitogenic and inflammatory cytokines are strongly implicated in the pathogenesis of psoriasis, alopecia areata, atopic dermatitis, and other potential autoimmune diseases of the skin. Inhibition of specific cytokine function using antibodies directed against the common p40 subunit of interleukin (IL)-12 and IL-23 has demonstrated proof-of-concept validating cytokine signaling as a therapeutic target for the treatment of psoriasis.

INCB018424 PHOSPHATE CREAM has been evaluated in over 200 subjects in 3 clinical studies with dosing of 1 to 3 months in duration. One study of 12 subjects with Alopecia Areata.

Pharmacodynamics:

Ex vivo addition of INCB018424 to the whole blood samples from psoriasis subjects inhibited cytokine-induced STAT3p levels with a similar potency to that observed previously in whole blood from healthy volunteers (IC₅₀ = 334 nM vs 414 nM, respectively). No significant inhibition of mean systemic STAT3p was observed in any cohort following topical INCB018424 application.

Pharmacokinetics:

Study 1:

- Cohort A: INCB018424 PHOSPHATE CREAM 0.5% versus vehicle applied QD.
- Cohort B: INCB018424 PHOSPHATE CREAM 1.0% versus vehicle applied QD.
- Cohort C: INCB018424 PHOSPHATE CREAM 1.5% versus vehicle applied BID.

Application of INCB018424 PHOSPHATE CREAM 0.5% to 1.5% QD or BID resulted in mean plasma concentrations of INCB018424 ranging from 0.34 ± 0.4 nM (Cohort A) through 2.10 ± 1.78 nM (Cohort C) at steady state. The mean INCB018424 steady-state concentration increased approximately proportional to application dose per day. The size of the lesion areas treated ranged from 9 to 63 cm². Application of INCB018424 PHOSPHATE CREAM 0.5% to 1.5% QD or BID resulted in a mean skin flux of INCB018424 ranging from 54 ± 41 ng/cm²/h (Cohort A) through 422 ± 200 ng/cm²/h (Cohort C). The mean skin flux of INCB018424 increased with increasing application (API) strength. The mean systemic bioavailability was $2.8 \pm 3.2\%$, $3.0 \pm 1.9\%$, $3.0 \pm 1.9\%$, $2.7 \pm 1.1\%$, and $2.7 \pm 2.3\%$ for Cohorts A through E, respectively. The systemic bioavailability of INCB018424 applied as a topical cream appears independent of the strength of the cream formulation.

Study 2:

- Cohort A: treat 2%-7% BSA with 1.5% BID in 5 subjects
- Cohort B: treat 8%-13% BSA with 1.5% BID in 5 subjects
- Cohort C: treat 14%-20% BSA with 1.5% QD in 5 subjects
- Cohort D (optional): treat 14%-20% of BSA with 1.0% QD or BID in 5 subjects
- Cohort E (optional): treat 14%-20% of BSA with 1.5% QD or BID in 5 subjects

The average plasma concentrations of INCB018424 for Cohort A, Cohort B, Cohort C, Cohort D, and Cohort E were 7.00 ± 2.11 nM, 29.38 ± 13.10 nM, 24.42 ± 10.07 nM, 34.96 ± 20.43 nM,

and 60.99 ± 73.85 nM, respectively, at the steady state. The mean INCB018424 C_{ss} increased approximately proportional to application dose per day. The mean skin flux of INCB018424 was estimated to be 180 ± 126 ng/cm²/h, 131 ± 92 ng/cm²/h, 60 ± 43 ng/cm²/h, 151 ± 126 ng/cm²/h, and 152 ± 74 ng/cm²/h, respectively, for Cohorts A, B, C, D, and E. The mean topical bioavailability was estimated to be $3.8 \pm 2.5\%$, $4.1 \pm 3.4\%$, $3.4 \pm 1.9\%$, $3.9 \pm 1.3\%$, and $5.2 \pm 1.9\%$, respectively, for Cohorts A, B, C, D, and E. Based on this result, it is concluded that the systemic bioavailability of INCB018424 applied as a topical cream is independent of the strength of the cream formulation and %BSA.

Study 3:

- Treatment A: INCB018424 PHOSPHATE CREAM 0.5% applied QD for 12 weeks
- Treatment B: INCB018424 PHOSPHATE CREAM 1.0% applied QD for 12 weeks
- Treatment C: INCB018424 PHOSPHATE CREAM 1.5% applied QD for 12 weeks
- Treatment D: Vehicle containing placebo cream applied QD for 12 weeks

Application of INCB018424 PHOSPHATE CREAM 0.5%, 1.0%, and 1.5% QD resulted in mean steady-state trough plasma concentrations ($C_{ss,min}$) of INCB018424 of 9.19 ± 11.77 nM, 16.99 ± 19.05 nM, and 19.97 ± 25.13 nM, respectively, for 0.5% QD to 1.5% QD. Thus, the mean INCB018424 $C_{ss,min}$ increased approximately proportional to application dose. As the severity of lesion thickness, erythema, and scale increased, the INCB018424 $C_{ss,min}$ appeared to be decreased for the same treatment. The subjects with less severe lesion thickness, erythema, and scale seemed to have higher trough INCB018424 exposures.

Study 4:

Twelve subjects were enrolled in Part A (1.5% BID). Pharmacokinetic data were available for 12 subjects at Week 4 and 5 subjects at Week 12. Application of INCB018424 PHOSPHATE CREAM 1.5% BID resulted in mean steady state plasma concentrations of 25.4 ± 15.9 nM at Week 4 and 43.0 ± 36.5 nM at Week 12, which are generally consistent with the steady state concentrations seen in subjects with psoriasis. Steady state was assumed to be achieved at Day 8.

6.2 Treatment Regimen

Subjects will apply the study drug topically to LP lesions twice daily. Treatment will take place from Day 0 to Week 8.

6.3 Preparation and Administration of Study Drug

The study drug will be supplied by Incyte to the Mayo Clinic Pharmacy, attn. [REDACTED], [REDACTED], Scottsdale, AZ [REDACTED]. The study drug will be stored in the Mayo Clinic Pharmacy. The study drug will be labelled in the Mayo Clinic Pharmacy and will be dispensed to the subjects. The subjects will be given the appropriate amount of topical cream to apply to the disease. Instructions on proper use will be provided to each subject.

6.4 Subject Compliance Monitoring

Compliance will be assessed through direct questioning of subjects as well as through drug use diaries. The drug tubes will be weighed, and weight will be documented at each visit to determine usage.

6.5 Prior and Concomitant Therapy

Individuals on stable doses of medications for chronic illnesses will be allowed. Individuals on immunosuppressive agents for LP will not be allowed; however, individuals on stable doses of immunosuppressant for other conditions will be allowed if deemed to be safe by the treating physicians. Additional exclusionary drugs are included in Table-1.

Individuals using INCB018424 PHOSPHATE CREAM should use topical broad spectrum sunscreens with a minimum of SPF30, avoid excess sunlight, and wear sun protective clothing.

6.6 Packaging

The drug will be packaged in 15 gram single tubes and bubble wrapped for shipment. The entire quantity needed for the study will be provided in one shipment. The study drug tubes will be labeled with a diaper label that fully surrounds the tube. All applicable US FDA required text will be included on the label, included Caution: Limited by U.S. Law to Investigational Use

6.7 Receiving, Storage, Dispensing and Return

6.7.1 Receipt of Drug Supplies

The drug will be obtained or delivered from Incyte Corporation to the pharmacy at each investigative site.

Upon receipt of the of the study treatment supplies, an inventory must be performed and a drug receipt log filled out by the person accepting the shipment. It is important that the designated study staff counts and verifies that the shipment contains all the items noted in the shipping invoice. Any discrepancies, damaged or unusable study drug in a given shipment (active drug or comparator) will be documented in the study files. The sponsor-investigator must be notified immediately of any discrepancies, damaged or unusable products that are received.

6.7.2 Storage

The INCB018424 PHOSPHATE CREAM drug product and placebo cream should be stored between 15°C and 30°C (59°F and 86°F). The supplies will be stored in the Mayo Clinic Pharmacy.

6.7.3 Dispensing of Study Drug

Regular study drug reconciliation will be performed to document drug assigned, drug dispensed, drug returns, and drug remaining. This reconciliation will be logged on the drug reconciliation form, and signed and dated by the study team.

6.7.4 Return or Destruction of Study Drug

At the completion of the study, there will be a final reconciliation of drug shipped, drug dispensed, drug returns, and drug remaining. This reconciliation will be logged on the drug reconciliation form, signed and dated. Any discrepancies noted will be documented and investigated, prior to return or destruction of unused study drug. Drug destroyed on site will be documented in the study files.

7 Study Procedures

7.1 Visit 1

Screening visit:

During this visit, we will do some tests and procedures to see if subjects are eligible to take part in this research study. The study staff will review the results of these tests and procedures. If subjects aren't eligible, the Principal Investigator will tell them why. At this visit we will:

- Ask about medical history
- Perform a physical exam, including height, weight, and “vital signs” (blood pressure, temperature, heart and breathing rates)
- Perform a chest x-ray
- Draw a blood sample
- We may take swabs to test for certain fungal and bacterial infections
- Test urine for pregnancy if female subject is able to become pregnant

If it isn't known if subject has HIV, Hepatitis B or C, blood tests will need to be done.

7.2 Visit 2

Day 0 Visit we will:

- Perform a physical exam, check vital signs and ask about side effects or health problems since last visit
- Exam skin lesions to note any changes
- Take photographs of skin lesions to document any changes
- Draw a blood sample
- Perform a skin biopsy (up to 3 tissue samples will be taken)
- Perform a tap stripping on skin
- Dispense study drug

7.3 Visit 3

Week 1 Visit we will:

- Perform a physical exam, check vital signs and ask about side effects or health problems since last visit
- Exam skin lesions to note any changes
- Take photographs of skin lesions to document any changes
- Draw a blood sample
- Dispense study drug

7.4 Visit 4

Week 2 Visit we will:

- Perform a physical exam, check vital signs and ask about side effects or health problems since last visit
- Exam skin lesions to note any changes
- Take photographs of skin lesions to document any changes
- Draw a blood sample
- Dispense study drug

7.5 Visit 5

Week 3 Visit we will:

- Give subject a physical exam, check vital signs and ask about side effects or health problems since last visit
- Exam skin lesions to note any changes
- Take photographs of skin lesions to document any changes
- Draw a blood sample
- Dispense study drug

7.6 Visit 6

Week 4 Visit we will:

- Perform a physical exam, check vital signs and ask about side effects or health problems since last visit
- Exam skin lesions to note any changes
- Take photographs of skin lesions to document any changes
- Draw a blood sample
- Perform a skin biopsy (up to 2 tissue samples will be taken)
- Perform a tap stripping on skin
- Dispense study drug

7.7 Visit 7

Week 8 Visit we will:

- Perform a physical exam, check vital signs and ask about side effects or health problems since last visit
- Exam skin lesions to note any changes
- Take photographs of skin lesions to document any changes
- Draw a blood sample

7.8 Visit 8

Week 12 Visit we will:

- Perform a physical exam, check vital signs and ask about side effects or health problems since last visit
- Exam skin lesions to note any changes
- Take photographs of skin lesions to document any changes
- Draw a blood sample

8 Statistical Plan

8.1 Sample Size Determination

Data analysis: Assuming a medium effect size (0.3) and a target power of 80%, a two-armed study would need about 108 subjects and a single arm about 88 subjects. Due to the costs associated with a study, we propose a single armed study of 12 subjects with corollary science including RNA sequencing. This will reduce costs and provide biomarkers predictive of response. Effect sizes will be estimated for the appropriate statistical tests that will be used for group comparisons in future studies. This will enable more accurate power and sample size estimates moving forward.

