4.1 General Description

This is a single center, exploratory, open-label, single-arm design study of 12 patients. Treatment naïve and treatment refractory patients with LP will be treated with INCB018424 PHOSPHATE CREAM. Patients who are non-responders, to physician choice standard of care, will undergo a washout period and will be enrolled in the study.

Multiple safety studies have been conducted with INCB018424 PHOSPHATE CREAM (see Safety) and a dose of 1.5% cream BID on up to 20% BSA is deemed safe. (Investigator's Brochure) The Within each cohort, the maximum reduction from baseline in the total psoriasis lesion assessment scores for the treated lesions was observed at the end of treatment (Day 28). (Investigator's Brochure) Therefore, we propose a single center, exploratory, open-label, single-arm design study of 12 patients. Treatment naïve and treatment refractory patients with LP will be treated with INCB018424 PHOSPHATE CREAM.

Individuals with LP involving less than 20% of the BSA will be eligible. Individuals must have 4 lesions at baseline, however, a minimum of 10 lesions is ideal, which are at least 5mm in diameter. 10 lesions are ideal as 2 lesions will be index lesions and 8 or more lesions will be selected from as responsive or non-responsive at 4 weeks. All lesions except for one index lesion will be treated and all lesions will be annotated, photographed, and scored. The rationale for a minimum of 8 lesions is based upon the assumption of a 50% response rate at 2 weeks. With 8 lesions, there would be a less than 1% chance that all 8 lesions would respond. Ideally, the 2 index lesions will be 10mm in diameter but this is not a requirement. Prior treatment will be allowed; however, a washout period of 2 weeks for topical and 4 weeks for systemic agents is required. At the washout period, individuals will undergo evaluation with a PGA, BSA calculation, and have the 2 largest, representative lesions selected for evaluation using a modified CAILS score lesion A- treatment index lesion and B-index control lesion. The determination of which lesion receives treatment and which is a control will be determined randomly. The additional lesions will be photographed, measured, scored, and recorded with Modified CAILS scores as well. The later calculations will be used for the determination of responsive and non-responsive lesions. Additional Pruritus measures using the NRS and Skindex-16 will be collected at that time.

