4.4 Primary Study Endpoints

Change in Modified CAILS of index treatment lesion and index control lesion (week 0 and 4) and change in lesion count (week 0 and week 4).

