8.2 Statistical Methods

Descriptive Statistics

Sample Size Computation and Power Analysis:

The sample size for this pilot study is set at 12 subjects for logistical and financial reasons. This is similar in size to other exploratory studies and will provide adequate data for estimation purposes for planning future studies. With 12 subjects, the study is intended to be for estimation purposes only.

Statistical Analysis Plan:

Data Analysis - The statistical analysis will provide descriptive summary statistics for categorical and continuous outcomes. Categorical variables will be described by their count and proportion of occurrence while continuous, normally distributed variables will be described by their mean and standard deviation; and continuous, non-normally distributed variables will be described by their median and range. The paired or unpaired Wilcoxon tests will be used to quantify differences in numerical outcomes while the Fisher's exact test and the McNemar's or Bowker's tests will be used to quantify changes in categorical variables.

If missingness occurs at random a mixed model will be utilized to assess the change in the lesion over time. A sensitivity analysis will be performed using the last observation carried forward and the results will be compared to that of the mixed-model.

Effect sizes will be estimated for the appropriate statistical tests that will be used for group comparisons in future studies. This will enable more accurate power and sample size estimates moving forward.

Bioinformatic Analysis:

RNA-seq analysis: We will use our recently developed LinNorm program (<https://www.bioconductor.org/packages/release/bioc/html/Linnorm.html>) to process RNA-seq data and detect differentially expressed genes (DEGs) by comparing the RNA-seq profiles. We will first find DEG between responsive and non-responsive samples from the same individual by using paired or unpaired Wilcoxon rank-sum test (depending on how the samples are collected). We will then rank each gene in the DEGs based on the occurrence frequencies in all 12 subjects

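### Sections 8.1 and 8.2 justify N=12 as estimation for planning later trials, but plan no confidence interval, state no precision, and for non-normal outcomes omit the SD of change that a later group comparison needs

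*Combined protocol and SAP*

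**What the plan says.** Section 8.1 gives sizes for a medium effect of 0.3 at 80% power: "a two-armed study would need about 108 subjects and a single arm about 88 subjects". It then sets 12 subjects on cost grounds, with RNA sequencing meant to supply predictive biomarkers. Both 8.1 and 8.2 state the use to be made of the data: "Effect sizes will be estimated for the appropriate statistical tests that will be used for group comparisons in future studies". Both add that later power and sample-size calculations will be more accurate as a result.

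Section 8.2 says the 12 subjects "will provide adequate data for estimation purposes for planning future studies", and continues: "With 12 subjects, the study is intended to be for estimation purposes only".

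The outputs listed in 8.2 are:
- counts and proportions for categorical outcomes;
- mean and SD for normally distributed outcomes, while "continuous, non-normally distributed variables will be described by their median and range";
- tests: "The paired or unpaired Wilcoxon tests will be used to quantify differences in numerical outcomes", with Fisher, McNemar or Bowker tests for categorical changes;
- a mixed model if data are missing at random, compared with last observation carried forward.

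The primary endpoint in Section 4.4 is "Change in Modified CAILS of index treatment lesion and index control lesion (week 0 and 4) and change in lesion count" from week 0 to week 4. On the two index lesions, Section 4.1 says: "The determination of which lesion receives treatment and which is a control will be determined randomly". No interval, standard error or target width appears anywhere.

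**The concern.** A study whose sample size rests on estimation should say how precise its estimates will be and report that precision. This plan does neither.

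The gap is widest for outcomes judged non-normal, which is a real prospect for an ordinal composite and a lesion count in 12 people. The median and range describe the sample. A Wilcoxon p-value does not measure how large a difference is or how well it is known. None of these gives the SD of change from which a later trial is sized.

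There is also a problem of transfer. The index comparison is within patient, treated lesion against control lesion, but the stated use is group comparisons. Going from one to the other needs the SD of change in each lesion and the correlation between the two lesions. The plan commits to reporting neither for non-normal outcomes, and never commits to the correlation.

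What is at stake is the size of the next trial. If one unstable number is carried forward without its interval, that trial could be several times too small or too large, with no warning to the reader.

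**Working it through.** **Inputs.** From 8.1: effect 0.3, power 80%, sizes 88 and 108, n = 12. Alpha is not stated; two-sided 5% is assumed. The metric of 0.3 is not stated, so two readings are carried through.

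**1. The plan's own figures.**
- *Standardised mean difference.* One sample: ((1.960 + 0.842)/0.3)² = 87.2, so 88, which matches. Two arms: 175 per arm, 350 in total (normal formula), which does not match 108.
- *Cohen's w in a chi-square test.* df 1: 87.2, so 88. df 2: 107.05, so 108. Both match.

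The pair therefore fits w = 0.3 better, but the documents do not settle it.

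**2. The 95% interval around 0.3 with n = 12.**
- *Paired standardised difference.* t = 0.3 × √12 = 1.039 on 11 df. The noncentrality values that put 1.039 at the 97.5th and 2.5th percentiles are -0.989 and 3.023. Dividing by √12 gives **-0.29 to 0.87**. Withdrawn subjects are not replaced (Section 5.4.1): with 11 subjects it is -0.31 to 0.90, and with 10 it is -0.34 to 0.93.
- *Cohen's w.* The chi-square statistic is 12 × 0.3² = 1.08. Inverting the noncentral chi-square gives **0 to 0.87** (df 1) or **0 to 0.78** (df 2).

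On either reading the interval runs from no effect to a very large one.

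**3. What that means for a later paired study** (paired t, 80% power):

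| Observed effect | 95% interval | N at estimate | N across interval |
|---|---|---|---|
| 0.3 | -0.29 to 0.87 | 90 | 13 to no upper limit |
| 1.0 | 0.29 to 1.69 | 10 | 5 to 99 |

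**4. How often the point estimate sizes a later study acceptably.** N is roughly proportional to 1/d², so the computed N is within a factor of two of the need when the estimate lies between δ/√2 and δ√2. Normal differences are assumed.
- *True 0.3* (0.212 to 0.424): the noncentral t gives 27%. Simulated pilots sized by the paired t formula give **28%** within a factor of two, 34% under half the need, and 38% over double or not computable (estimate at or below 0.05).
- *True 1.0* (0.707 to 1.414), for a future group comparison with the correlation held fixed: **65%** within a factor of two, 18% under half, 17% over double.

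**5. From paired to between-group.** With equal SDs, d = dz × √(2(1 − ρ)), where ρ is the within-patient correlation of the two lesions' changes. For dz = 0.3:

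| ρ | d | Two-arm total |
|---|---|---|
| 0 | 0.424 | 178 |
| 0.5 | 0.300 | 352 |
| 0.8 | 0.190 | 876 |

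The same paired result implies totals that differ almost fivefold (876/178 = 4.9), depending on a quantity the plan does not say it will report.

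**6. Precision that could have been stated.** The half-width of a 95% t interval with 12 pairs is 2.201/√12 = 0.635, or about **0.64 SD** of the paired difference.

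**The case against.** The plan is open about being a cost-limited pilot and claims nothing beyond estimation. For an outcome summarised by mean and SD, a reader who knows n = 12 can build the t interval: mean ± 0.635 SD. A standardised effect with its n likewise fixes its noncentral-t interval. The mixed model would ordinarily produce standard errors. So a reader who infers that no uncertainty could ever be recovered goes too far.

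Much of that stands, with limits. The mean-and-SD route covers only outcomes judged normal, and works for the index contrast only if the SD is that of the within-patient difference, which 8.2 does not specify. The mixed model depends on a missing-data condition and carries no commitment to report an interval. Non-normal outcomes remain uncovered.

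Three other strong readings are not supported:
- *Estimation is the study's sole statistical aim.* Section 8.2 comes close to saying so, but 8.1 also names predictive biomarkers and 8.2 plans tests and RNA-seq inference.
- *The -0.29 to 0.87 interval belongs to the protocol's 0.3.* The protocol names no metric, and its two sizes fit Cohen's w.
- *Twelve is the wrong number.* A logistical limit is a legitimate basis for a pilot, and 88 and 108 do not determine it. The defect is in what will be reported.

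**Conclusion.** The concern holds as a gap between stated purpose and planned output. N=12 is justified by estimation for later studies, but no interval is planned, no precision is stated, and non-normal outcomes would lack the SD of change.

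The promise of more accurate future sample sizes is not supported at the effect the protocol names: about 28% of pilots land within a factor of two. At a true effect of 1.0 the figure for a group comparison is about 65%, better but still wrong by more than double or half in about a third of pilots.

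These figures assume two-sided 5%, 80% power, normal paired differences and all 12 subjects evaluable. The 28% and 65% also rest on 0.3 and 1.0 being standardised paired differences, and on a factor of two as the criterion, which is a reviewer's choice. The absence of an interval and a precision statement depends on none of these assumptions. This should be changed; it does not invalidate the study.

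**What to change.** Keep N=12.

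**Section 8.2.** For each primary endpoint, make the reported result an estimate with its 95% confidence interval:
- the within-patient difference, treated minus control index lesion, in week 0 to week 4 change in Modified CAILS. Section 4.4 lists the two lesions but does not define this contrast;
- the week 0 to week 4 change in lesion count.

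Fix one method in advance, for example the Hodges-Lehmann estimate with the signed-rank interval, which matches the planned Wilcoxon test. Whatever the distribution, also report the mean and SD of change for each index lesion and the within-patient correlation. Give standardised effect sizes with 95% intervals, treat p-values as descriptive, and show future sample sizes across the interval, not at the point estimate alone.

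**Section 8.1.** Replace the claim of greater accuracy with the expected precision: a 95% half-width of about 0.64 SD of the paired difference with 12 pairs. If the 88 and 108 stay, state their metric, test, alpha, endpoint, and whether 108 is a total or per arm.

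**Section 4.1.** One paragraph leaves one index lesion untreated; a later one starts treatment on all LP lesions. The two must be reconciled, because the contrast is valid only if the control lesion is what the analysis takes it to be.

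**Cost.** Edits to these sections and a few lines in the results tables. The analysis and reporting changes alter neither the sample size, the visits nor the data collected.
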